#### 3.3.4.4 *Lab evaluations*

Handling of the safety lab variables will be the same as the PD variables (section 3.3.3.5)

#### 3.3.4.5 *Injection site reaction*

## EXTBIO EXT608-101 Statistical Analysis Plan, V2, 2023-JULY-04

Injection site Assessment includes Tenderness, VAS pain score, Edema and Erythema.

- If Tenderness is “None” and VAS pain score is missing, then VAS pain score will be set as 0
- No substitution will be done for any missing VAS if Tenderness is not None.

Although the standard VAS line is 100mm, the actual VAS line printed on paper could be deviate from 100mm due to printer settings. Thus, all reported VAS will be normalized to 100mm scale for analyses.

The normalized VAS ( $VAS_{nom}$ ) score is calculated as below:

$$VAS_{nom} = \frac{Measured\ VAS(mm) \times 100}{Total\ VAS(mm)}$$

The following describes the handling of Edema and Erythema related variables.

- If “none” reported for edema or Erythema, then the following variables will be substitute as 0 for analyses only
  - Shortest length (Edema or Erythema)
  - Longest length (Edema or Erythema)
  - Tallest height (Edema)
  - Grade (Erythema)
- If “not done” reported, there is no substitution

Edema and Erythema is assumed to be Ellipse, and the area will be calculated as:

$$Area\ of\ Edema\ or\ Erythema = \frac{(3.14159 \times \text{shortest\ length} \times \text{longest\ length})}{4}$$

The Grade of Erythema is expected to be the following:

- 1: very faint, 2: faint, 3: bright, 4: very bright
- If a non-integer number is reported, it will be rounded to the nearest integer.

The tallest height of Edema will be used directly.

### 3.3.4.6 Immunogenicity variables

Immunogenicity variables include anti-drug antibodies (ADA) and any neutralizing subset (NAb). These are variables for exploratory analysis. Handling of these variables will not be pre-defined in this analyses plan.

## EXTBIO EXT608-101 Statistical Analysis Plan, V2, 2023-JULY-04

### 3.4 STATISTICAL METHODS

#### 3.4.1 General Considerations for all analyses

Unless specified, the following will apply to all summary tables:

- Continuous variable descriptive summary will include N, Mean, median, standard deviation, maximum and minimum.
- Categorical variable descriptive summary will include Total, count, and percentage.

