### **Statistical Analyses**

AEs will be presented in listings and TEAEs will be summarized. Individual results of laboratory tests (hematology, chemistry, and urinalysis) will be listed and change from baseline will be summarized using shift tables. Individual results of vital signs will be listed and observed values and changes from baseline will be summarized.

Individual results of quantitative ECG parameters from the 12-lead safety ECGs will be listed and observed values and changes from baseline will be summarized and analyzed consistent with the ICH E14 (3).

All summaries will be performed by placebo and each EXT608 dose level. Placebo data will be pooled across cohorts. Physical exam findings will be presented in data listings.

Concentrations of EXT608 will be summarized by dose over each scheduled sampling time using descriptive statistics. Individual plasma concentration data versus time will be presented in a data listing. PK parameters will be summarized by dose using descriptive statistics. Dose proportionality will be assessed graphically and using a power model. PD will be presented in listings and summarized by dose and time point.

Detection of ADA and NAbs will be presented in listings and summarized by dose and time point.

No formal hypothesis testing will be conducted as part of this study.

DMB data packages will be based on the FAS for safety and PP for PK/PD.

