### 8.3 Data Analysis

AEs will be presented in listings and Treatment Emergent Adverse Events (TEAEs) will be summarized. Individual results of laboratory tests (hematology, chemistry, and urinalysis) will be listed and change from baseline will be summarized using shift tables. Individual results of vital signs will be listed and observed values and changes from baseline will be summarized.

Individual results of quantitative ECG parameters from the 12-lead safety ECGs will be listed and observed values and changes from baseline will be summarized and analyzed consistent with the ICH E14 (3).

All summaries will be performed by placebo and each EXT608 dose level. Placebo data will be pooled across cohorts. Physical exam findings will be presented in data listings.

Concentrations of EXT608 will be summarized by dose over each scheduled sampling time using descriptive statistics. Individual plasma concentration data versus time will be presented in a data listing. PK parameters will be summarized by dose using descriptive

statistics. Dose proportionality will be assessed graphically and using a power model. PD will be presented in listings and summarized by dose and time point.

Detection of ADA and NAbs will be presented in listings and summarized by dose and time point.

No formal hypothesis testing will be conducted as part of this study.

DMB data packages will be based on the FAS for safety and PP for PK/PD.

Further details are described in the Statistical Analysis Plan.

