**1.4 MODIFICATIONS FROM THE STATISTICAL SECTION IN THE PROTOCOL**

None

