### ***3.4.4.1 PK Analyses***

All PK parameters (section 3.3.3.2) will be presented descriptively for each treatment arm.

A simple ANOVA model with treatment arm as the factor will be applied to each PK parameter to compare the active treatment arms to the pooled placebo group. The estimated mean difference and 95% Confidence Interval between each treatment arm and the placebo group will be presented. The corresponding p-value will also be reported although we do not expect it to be significant given the small sample size.

Additionally, a statistical model will be attempted to model the dose response of each PK parameters. The mode will not be pre-defined. We will plot the mean of each PK parameter against the dose and find an appropriate model if any.

- In addition to the Safety/FAS population, it will also be done with the PP population

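### The SAP plans no geometric mean or geometric CV% for PK exposure and picks a dose model from a plot of arm means, while the protocol promises a power model

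*SAP*

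**What the plan says.** SAP 3.4.1 opens with "Unless specified, the following will apply to all summary tables" and gives the list for continuous variables: "Continuous variable descriptive summary will include N, Mean, median, standard deviation, maximum and minimum".

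SAP 3.4.4.1 then says: "All PK parameters (section 3.3.3.2) will be presented descriptively for each treatment arm". It names no PK-specific statistics, so the 3.4.1 list applies. (The cross-reference leads to the baseline and LLOQ rules; the parameters themselves are defined in SAP 3.3.3.4.) No geometric mean or geometric CV% is planned anywhere in the SAP text.

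On dose, Protocol 8.3 says: "Dose proportionality will be assessed graphically and using a power model". SAP 3.4.4.1 does not name that model. It leaves the model open and says: "We will plot the mean of each PK parameter against the dose and find an appropriate model if any". Under 3.4.1 that mean is the arithmetic one. SAP 1.4, headed "MODIFICATIONS FROM THE STATISTICAL SECTION IN THE PROTOCOL", lists none.

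**The concern.** Exposure parameters are positive and usually right-skewed. A power model, parameter = a × dose^b, is normally fitted as a straight line in logs, and the centre of an arm on that scale is the geometric mean. The SAP already works in logs within each participant: 3.3.3.4.4 regresses log concentration on time, and 3.3.3.4.7 derives the late half-life from exponential decline. Between participants it goes back to the arithmetic scale.

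Two things are at stake. First, single-dose PK is the first secondary objective, and Protocol 1.2 says the data are meant to help choose dose levels for later patient studies. With three active participants per cohort, one high value moves the arithmetic mean visibly. Second, the protocol committed to a dose-proportionality model, whereas the SAP would choose one after seeing a plot of arm means. A reader comparing the two documents cannot tell which analysis will be reported.

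**Working it through.** **The plan's own figure.** The only relevant number is the design count: 6 cohorts × 4 = 24 participants, of whom 6 × 3 = 18 are active and 6 × 1 = 6 placebo. This matches the approximately 24 evaluable participants in Protocol 3.1.1 and SAP 2.1.1. The documents state no mean, SD or CV for any PK parameter.

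**Inputs.** Active n per cohort = 3 (SAP 2.1.1). Between-participant CV is an assumption, taken as 30 to 100% with a lognormal distribution.

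**Step 1: gap between the two means.** Put the population geometric mean at 1 and s² = ln(1 + CV²).

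- Expected sample arithmetic mean: exp(s²/2), whatever n is.
- Expected sample geometric mean: exp(s²/(2n)), which is exp(s²/6) at n = 3.
- Ratio at n = 3: exp(s²/2 − s²/6) = exp(s²/3) = (1 + CV²)^(1/3).

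| CV | s² | Population ratio exp(s²/2) | Ratio at n = 3, exp(s²/3) |
|---|---|---|---|
| 30% | 0.086 | 1.04 | 1.029 |
| 50% | 0.223 | 1.12 | 1.077 |
| 70% | 0.399 | 1.22 | 1.142 |
| 100% | 0.693 | 1.41 | 1.260 |

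Simulation of 400,000 arms of three per CV agrees with the last column. Within a single arm the ratio is skewed: at CV 50% its median is 1.05 and its 95th percentile 1.24; at CV 100% these are 1.17 and 1.82.

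**Step 2: is the arithmetic mean biased?** At CV 50% the population mean is exp(0.223/2) = 1.118, and the simulated average of the sample mean is 1.119. It is unbiased for its own target.

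**Step 3: can the geometric mean be recovered from the planned table?** With three values, the minimum, median and maximum are the data. For illustrative values 50, 80 and 150, the geometric mean is (50 × 80 × 150)^(1/3) = 84.3, against an arithmetic mean of 93.3. This fails if a dose is repeated under Protocol 3.1.5, which gives 3 + 3 = 6 active participants. Four inner values are then unknown, and the mean, SD and median supply only three equations.

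**Step 4: effect on a log-log slope fitted to arm means.** Assumed: six doses 3-fold apart, three active participants each, true slope 1, 60,000 simulated trials per scenario. CV is either constant or changes linearly from the lowest to the highest dose.

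| CV across doses | Slope from arithmetic means | Slope from geometric means |
|---|---|---|
| Constant at 30, 50 or 100% | 1.00 | 1.00 |
| 60% falling to 20% | 0.985 | 1.00 |
| 20% rising to 60% | 1.016 | 1.00 |
| 100% falling to 30% | 0.967 | 1.00 |

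With constant CV the gap from Step 1 is the same at every dose, so it goes into the intercept and leaves the slope alone.

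**The case against.** The case on the other side is substantial, and most of it stands.

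- **The planned list is fuller than mean and SD.** It includes median, minimum and maximum. Under lognormality the population median equals the geometric mean, and at n = 3 a reader can compute the geometric mean by hand. This stands for single cohorts, but not for a repeated dose.
- **Tmax needs nothing.** Its median and range are already planned.
- **A power model fitted to individual log values does not use the descriptive table.** True, but the SAP does not plan that fit. It selects a model from arm means, which is where the choice of mean can matter.
- **No decision turns on this.** Escalation under Protocol 3.1.5 rests on Grade 3 adverse events and serum calcium, and Protocol 8.3 rules out formal hypothesis testing. This stands.
- **Table layouts may say more.** SAP section 4 refers to an attached file that is not available here. It might add rows, but the SAP text does not say so.

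A reader might infer that reported exposures will be inflated. The documents do not support that: the arithmetic mean is a different summary, not a biased one, and the size of the gap depends on a CV they do not give. Nor should the population ratios, 4 to 41%, be quoted for arms of three, where the average gap is about 3 to 26%. A reader might also object that mean minus 2 SD can fall below zero. In simulated arms of three that happens about 5% of the time at CV 30% and 66% at CV 100%, but no section plans to report that quantity.

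**Conclusion.** The point holds as a minor reporting and specification gap with two parts. Exposure parameters lack the summary that matches the scale of the promised model. The model itself has also dropped out of the SAP without being declared as a change.

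Assuming lognormal exposure with CVs of 30, 50, 70 and 100%, the arithmetic mean sits on average about 3, 8, 14 and 26% above the geometric mean at n = 3. The slope of a log-log fit to arm means does not move if CV is constant, and lay between about 0.97 and 1.02 in the scenarios where CV drifts with dose. The CVs, the 3-fold dose spacing and the linear drift are all assumptions.

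It would be tempting to conclude that the descriptive tables contradict the power model or distort dose proportionality. That goes too far: the tables do not enter a model fitted to individual values, and the slope shifts found here are small. Sample size and the escalation rules are unaffected.

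**What to change.** Add to SAP 3.4.4.1:

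> AUCs, Cmax, CL/F, Vz/F and half-life will additionally be summarized by geometric mean and geometric CV%. Dose plots will show individual values and geometric means on log-log axes. Dose proportionality of AUC and Cmax will be assessed by the protocol's power model fitted to individual log values, reporting the slope and its CI.

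This would replace the sentence that picks a model from the plot of means. If the sponsor prefers another dose model, SAP 1.4 should list it as a departure from Protocol 8.3. The arithmetic rows can stay, and Tmax needs no change. The cost is three sentences in the SAP and a few lines of code, with no extra data and no loss of any planned output.

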#### 3.4.2 Disposition of Participants

Descriptive summaries of participants' disposition will be provided. It will show the count and percentage.

The following will be presented for all screened participants:

- Screen failed
- Enrolled (qualified)
- Randomized

The following will be presented for all randomized participants:

- Cohorts
- Fully completed
- Early terminated
- Safety/FAS Population
- PP Population
- Treatment Randomized
- Treatment Received

#### 3.4.3 Demographic Characteristics analyses

The demographic characteristics analyses will be done for Safety/FAS population.

##### 3.4.3.1 Demographics

Descriptive summaries of the following will be provided:

- Age
- Race
- Ethnicity
- BMI

##### 3.4.3.2 Medical History

Descriptive summaries of Body System will be provided.

##### 3.4.3.3 Physical Exam

Descriptive summaries of Body System will be provided.

## EXTBIO EXT608-101 Statistical Analysis Plan, V2, 2023-JULY-04

Additionally, change from baseline of the status of each Physical Exam will be summarized for each treatment arm.

### ***3.4.3.4 Height, Weight and BMI***

Height, weight and BMI will be summarized descriptively for each treatment arm at screen visit.

Additionally, weight will be summarized at each time point for each treatment arm from baseline.

### ***3.4.3.5 Medication***

Only a listing of the medication used by each participant will be provided.

It will be done for safety population only.

### ***3.4.3.6 Protocol Compliance***

The protocol compliance summary can be inferred from the disposition summary in section 3.4.2. Thus, there is no separated analysis.

## **3.4.4 Efficacy Analysis**

All Efficacy analyses will be done for Safety/FAS population unless specified.

### ***3.4.4.1 PK Analyses***

All PK parameters (section 3.3.3.2) will be presented descriptively for each treatment arm.

A simple ANOVA model with treatment arm as the factor will be applied to each PK parameter to compare the active treatment arms to the pooled placebo group. The estimated mean difference and 95% Confidence Interval between each treatment arm and the placebo group will be presented. The corresponding p-value will also be reported although we do not expect it to be significant given the small sample size.

Additionally, a statistical model will be attempted to model the dose response of each PK parameters. The mode will not be pre-defined. We will plot the mean of each PK parameter against the dose and find an appropriate model if any.

- In addition to the Safety/FAS population, it will also be done with the PP population

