### ***3.3.3.2 PK values at baseline, infinity, and under Lower Limitation of Qualification (LLOQ)***

PK is assumed to be 0 at baseline (i.e. prior to time 0) and at infinity.

Additionally, any PK value that is LLOQ between time 0 and infinity will be assumed to be:

- 1/2 of the value of LLOQ specification (specified in the comment for PK results by Lab), or
- 100pg/mL, if no LLOQ specification is given (default is 200 pg/mL)

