### ***3.3.3.4 PK Parameters***

The following PK parameters will be developed directly from the PK data.

- PK parameters will only be calculated or evaluated for participants who receives EXT608 dose. PK parameters will not be calculated for placebo participants.

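### The SAP's placebo comparison of PK parameters has an empty reference group, and the protocol's power model for dose proportionality is not carried into the SAP

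*SAP*

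**What the plan says.** SAP 3.4.4.1 contains three PK analyses.

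- Descriptive summaries: "All PK parameters (section 3.3.3.2) will be presented descriptively for each treatment arm".
- A one-way ANOVA with arm as the factor, "applied to each PK parameter to compare the active treatment arms to the pooled placebo group". It is to give a mean difference and 95% CI for each arm against placebo, and the SAP adds: "The corresponding p-value will also be reported although we do not expect it to be significant given the small sample size".
- A dose-response model whose form is expressly left open: "We will plot the mean of each PK parameter against the dose and find an appropriate model if any".

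On which participants have PK parameters, SAP 3.3.3.4 limits the calculation to EXT608 recipients and adds that "PK parameters will not be calculated for placebo participants".

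The protocol takes a different line on the last two analyses. Section 8.3, like the synopsis, says "Dose proportionality will be assessed graphically and using a power model" and also "No formal hypothesis testing will be conducted as part of this study". It refers the reader to the SAP for further detail. SAP 1.4, which is there to record changes from the protocol's statistical section, records none.

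**The concern.** Two sections of the SAP cannot both be followed. One compares every EXT608 arm with placebo on every PK parameter; the other says placebo participants have no PK parameters. Whoever programs the analysis must either drop a planned output or invent placebo values that the SAP does not define.

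The SAP's remark on significance puts the difficulty down to small numbers. The obstacle is the absence of any data in the reference group, and a larger trial would have the same problem. The p-values have no alpha level or decision rule attached, but they sit awkwardly beside the protocol's statement that no formal testing is done.

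The dose-exposure relationship is the informative PK question in a single ascending dose study. The protocol fixes a model for it. The SAP text gives no functional form, no list of parameters to be fitted and no interval for the exponent, and it describes a model picked after looking at the means.

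A smaller slip is in the same place. Section 3.4.4.1 points to 3.3.3.2 for the PK parameters, but that section deals with baseline and below-LLOQ values ("PK is assumed to be 0 at baseline (i.e. prior to time 0) and at infinity"). The parameters are defined in 3.3.3.4.

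**Working it through.** **Head count.** Up to 6 cohorts of 4, allocated 3 EXT608 to 1 placebo (SAP 2.1.1): 6 × 4 = 24, of which 6 × 3 = 18 receive EXT608 and 6 × 1 = 6 receive placebo. This matches the approximately 24 evaluable participants in the plan. The documents give no alpha, power, effect size or SD, so there is no power calculation to reproduce.

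**Estimability of the placebo contrasts.** Write the ANOVA with an intercept (placebo as reference) and one indicator for each of 6 EXT608 arms, giving 7 columns.

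- If all 6 placebo participants had PK parameters: 24 rows, rank 7, 24 − 7 = 17 error df, and all 6 contrasts estimable.
- Under SAP 3.3.3.4: 18 rows, 0 placebo rows, rank 6. A contrast is estimable only if it lies in the row space of the design matrix. Adding any one arm-minus-placebo contrast as a row raises the rank from 6 to 7, so 0 of 6 is estimable. Only differences between EXT608 arms remain, on 18 − 6 = 12 error df.

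This result needs no assumption about variability or dose path.

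**Could imputation rescue it?** SAP 3.3.3.2 sets PK to 0 at baseline and to half the LLOQ for later values below it. That rule concerns concentrations, and 3.3.3.4 rules out deriving placebo parameters at all. If placebo parameters were nevertheless set to a constant such as 0, a group with no variation would add 5 error df and no error sum of squares. The pooled MSE would be multiplied by 12/17 = 0.71 and the SD by √0.71 = 0.84. The contrast would then ask only whether a dosed arm differs from that constant.

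**Is the protocol's power model workable at this size?** The model is ln(parameter) = a + b·ln(dose), fitted to individual EXT608 participants.

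- From the documents: starting dose 4 µg and no step above 3-fold (Protocol 3.1.2), the 2-fold and 3-fold steps of Protocol 3.1.5, and 3 EXT608 participants per cohort.
- Assumed: six distinct dose levels (five steps), so 18 participants and 16 residual df; quantifiable exposure at every level; CV of 20%, 30% or 50%. The dose paths serve the arithmetic only.
- Formulas: σ = √ln(1 + CV²), which gives 0.198, 0.294 and 0.472; Sxx = 3·Σ(ln d − mean)²; SE(b) = σ/√Sxx; 90% half-width = t(0.95, 16) × SE(b), with t = 1.746.

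| Dose path (µg) | Sxx | Half-width, CV 20% | CV 30% | CV 50% |
|---|---|---|---|---|
| Five 3-fold steps, 4 to 972 | 63.36 | 0.043 | 0.064 | 0.104 |
| Two 3-fold then three 2-fold, 4 to 288 | 37.91 | 0.056 | 0.083 | 0.134 |
| Five 2-fold steps, 4 to 128 | 25.22 | 0.069 | 0.102 | 0.164 |

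First cell worked: 1.746 × 0.198/√63.36 = 0.043.

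Protocol 3.1.5 also allows repeat cohorts and 1.5-fold steps, and six cohorts is a maximum. The path 4, 12, 24, 48, 48, 72 gives 0.08, 0.12 and 0.20. Four cohorts at 4, 8, 16, 32 (12 participants, 10 df) give 0.13, 0.20 and 0.32.

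**The case against.** The strongest reply is that the ANOVA error does no harm. A contrast that cannot be estimated yields no wrong number, the output is simply dropped, and this is a secondary analysis in a study not sized for inference. That is right about the consequence if the software is left to fail, and it is why the point ranks no higher than it does. It does not cover the case where someone supplies placebo values to make the procedure run, and a planned analysis that cannot be produced still has to be corrected.

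The second reply is that the protocol's power model still stands. SAP 1.4 declares no modifications, and the open-ended model is introduced as an addition. This reading is possible, and the text does not settle whether the SAP under-specifies the protocol's model or departs from it without saying so. On either reading the parameters to be fitted and the interval to be reported are not stated, in the document to which the protocol defers for detail.

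Third, SAP section 4 refers to a separate list of tables that is not among the documents reviewed, and it may include a power-model output. That could narrow the second point. It could not resolve the conflict between 3.3.3.4 and 3.4.4.1.

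Fourth, p-values without a decision rule are arguably not formal testing. This is fair: they are a poor fit with the protocol rather than a plain contradiction.

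Finally, the precision figures describe the remedy and not the damage, and they depend on six distinct dose levels. Both statements are correct, and the figures should be read that way.

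**Conclusion.** The concern holds and should be fixed. As written, 0 of the 6 arm-versus-placebo contrasts can be estimated for any PK parameter, which follows directly from the two SAP sections. The power model named in the protocol does not appear in the SAP text, which describes a model chosen after the data are plotted. Whether that is missing detail or an undeclared change cannot be decided from the documents.

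The effect is confined to the secondary PK objective. The primary safety objective, the escalation decisions and the descriptive PK summaries are untouched. A plot of means against dose and some dose-response modelling are planned, so the topic is not absent.

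The power model is practicable. Under the stated assumptions the 90% half-width for the exponent runs from 0.04 to 0.16 with six distinct dose levels, and reaches about 0.32 in the four-cohort example at a CV of 50%. Half-LLOQ substitution at low doses could add bias; the documents do not show whether it would arise.

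**What to change.** In SAP 3.4.4.1:

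1. Delete the ANOVA against placebo for PK parameters, with its differences, intervals and p-values.
2. State the power model, ln(parameter) = a + b·ln(dose), fitted to individual EXT608 participants for Cmax and the AUCs. Report b with a confidence interval at a stated level. The documents do not fix the level; 90% was used above for illustration.
3. Keep the plot against dose. Label any other dose-response model exploratory and record it in SAP 1.4.
4. Change the cross-reference for PK parameters from 3.3.3.2 to 3.3.3.4.

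The cost is SAP wording only. No new data are needed and one analysis is removed.
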